5.2. Exclusion Criteria

A subject will not be eligible for inclusion in this study if any of the following criteria apply:

CONCURRENT CONDITIONS/MEDICAL HISTORY (INCLUDES LIVER FUNCTION AND QTc INTERVAL)

1. **Concurrent Respiratory Disease:** Presence of a known pre-existing, clinically important lung condition other than asthma. This includes current infection, bronchiectasis, pulmonary fibrosis, bronchopulmonary aspergillosis, or diagnoses of emphysema or chronic bronchitis (chronic obstructive pulmonary disease other than asthma) or a history of lung cancer.
2. **Eosinophilic Diseases:** Subjects with other conditions that could lead to elevated eosinophils such as Hypereosinophilic Syndromes, including Churg-Strauss Syndrome, or Eosinophilic Esophagitis. Subjects with a known, pre-existing parasitic infestation within 6 months prior to Visit 1 are also to be excluded.
3. **Malignancy:** A current malignancy or previous history of cancer in remission for less than 12 months prior to screening (Subjects that had localized carcinoma of the skin which was resected for cure will not be excluded).
4. **Immunodeficiency:** A known immunodeficiency (e.g. human immunodeficiency virus – HIV), other than that explained by the use of corticosteroids taken as therapy for asthma.
5. **Other Concurrent Medical Conditions:** Subjects who have known, pre-existing, clinically significant cardiovascular, endocrine, autoimmune, metabolic, neurological, renal, gastrointestinal, hepatic, haematological or any other system abnormalities that are uncontrolled with standard treatment.
6. **Liver Disease:** Known, pre-existing, unstable liver disease (as defined by the presence of ascites, encephalopathy, coagulopathy, hypoalbuminaemia, esophageal or gastric varices or persistent jaundice), cirrhosis, and known biliary abnormalities (with the exception of Gilbert's syndrome or asymptomatic gallstones).
7. **ECG Assessment:** QT interval corrected for heart rate by either Fridericia's or Bazett's formula $QTc(F)/QTc(B) \geq 450\text{msec}$ or $QTc(F)/QTc(B) \geq 480\text{ msec}$ for subjects with Bundle Branch Block at Visit 1.

CONCOMITANT MEDICATIONS

8. **Xolair:** Subjects who have received omalizumab within 130 days of Visit 1.
9. **Other Monoclonal Antibodies not including mepolizumab:** Subjects who have received any monoclonal antibody (other than Xolair) to treat inflammatory disease within 5 half-lives of Visit 1.

- | |
|--|

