14.8. Appendix 8: List of Data Displays

14.8.1. Study Population Tables

Study Population - Tables					
No.	Population	IDSL / TST ID / Example Shell	Title	Programming Notes	Deliverable [Priority]
6.1	ASE	TAB_POP1	Summary of Study Populations		SAC
6.2	ASE	ES6	Summary of Screen Failures	Include footnote "Note: Inclusion/exclusion criteria include protocol defined continuation criteria."	SAC
6.3	ASE	NS1	Summary of Number of Subjects by Country and Site	"Not Treated" column should be added to include subjects who did not receive treatment.	SAC
6.4	All Subjects	SD1	Summary of IP Discontinuation		SAC
6.5	All Subjects	ES1	Summary of Subject Disposition		SAC
6.6	All Subjects	DV1	Summary of Important Protocol Deviations		SAC
6.7	All Subjects	EX1	Summary of Exposure to Study Treatment (months)	Categories 1, 2, 3 months Summary statistics for duration of exposure (months)	SAC
6.8	All Subjects	TAB_EX1	Summary of Injection Site by Visit		SAC
6.9	All Subjects	DM1	Summary of Demographic Characteristics		SAC
6.10	All Subjects	DM5	Summary of Race and Racial Combinations		SAC
6.11	ASE	DM11	Summary of Age Ranges	"Not Treated" column should be added to include subjects who did not receive treatment.	SAC
6.12	All Subjects	TAB_POP2	Summary of Disease Duration		SAC
6.13	All Subjects	TAB_POP3	Summary of Prior Experience with Self-Injection of Medication		SAC
6.14	All Subjects	TAB_POP4	Summary of Baseline Mepolizumab Use		SAC
6.15	All Subjects	MH1	Summary of Past Medical Conditions		SAC
6.16	All Subjects	MH1	Summary of Current Medical Conditions		SAC
6.17	All Subjects	FH1	Summary of Family History of Cardiovascular Risk Factors		SAC

Study Population - Tables					
No.	Population	IDSL / TST ID / Example Shell	Title	Programming Notes	Deliverable [Priority]
6.18	All Subjects	SU1	Summary of Smoking History	Smoking status (current/former/never) only	SAC

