11.18	All Subjects	AE1	Summary of All Pre-Treatment Serious Adverse Events by System Organ Class and Preferred Term		SAC
11.19	All Subjects	AE1	Summary of All Drug-Related Serious Adverse Events by System Organ Class and Preferred Term		SAC

CONFIDENTIAL

205667

No.	Population	IDSL / TST ID / Example Shell	Title	Programming Notes	Deliverable [Priority]
Safety : Tables					
Adverse Events of Special Interest					
11.20	All Subjects	AE1	Summary of On-Treatment Adverse Events Reported by the Investigator as Meeting the Criteria for Anaphylaxis		SAC
11.21	All Subjects	TAB_S1	Summary Profile of On-Treatment Adverse Events Reported by the Investigator as Meeting the Criteria for Anaphylaxis		SAC
11.22	All Subjects	AE1	Summary of On-Treatment Adverse Events Defined by the Investigator as Systemic Reactions - Allergic (Type I Hypersensitivity) and Other Systemic		SAC
11.23	All Subjects	TAB_S1	Summary Profile of On-Treatment Adverse Events Defined by the Investigator as Systemic Reactions - Allergic (Type I Hypersensitivity) and Other Systemic		SAC
11.24	All Subjects	AE1	Summary of On-Treatment Adverse Events Defined by the Investigator as Systemic Reactions - Allergic (Type I Hypersensitivity)		SAC
11.25	All Subjects	TAB_S1	Summary Profile of On-Treatment Adverse Events Defined by the Investigator as Systemic Reactions - Allergic (Type I Hypersensitivity)		SAC
11.26	All Subjects	AE1	Summary of On-Treatment Adverse Events Defined by the Investigator as Systemic Reactions – Other Systemic		SAC
11.27	All Subjects	TAB_S1	Summary Profile of On-Treatment Adverse Events Defined by the Investigator as Systemic Reactions - Other Systemic		SAC
11.28	All Subjects	AE1	Summary of On-Treatment Adverse Events Defined by the Investigator as Local Injection Site Reactions		SAC

CONFIDENTIAL

205667

No.	Population	IDSL / TST ID / Example Shell	Title	Programming Notes	Deliverable [Priority]
Safety : Tables					
11.29	All Subjects	TAB_S1	Summary Profile of On-Treatment Adverse Events Defined by the Investigator as Local Injection Site Reactions		SAC
11.30	All Subjects	AE1	Summary of On-Treatment Adverse Events Categorised as Serious Cardiac, Vascular and Thromboembolic Events		SAC
11.31	All Subjects	TAB_S1	Summary Profile of On-Treatment Adverse Events Categorised as Serious Cardiac, Vascular and Thromboembolic Events		SAC
11.32	All Subjects	AE1	Summary of On-Treatment Adverse Events Categorised as Serious Ischemic Events		SAC

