11.33	All Subjects	TAB_S1	Summary Profile of On-Treatment Adverse Events Categorised as Serious Ischemic Events		SAC
11.34	All Subjects	AE1	Summary of On-Treatment Adverse Events Categorised as Malignancies		SAC
11.35	All Subjects	TAB_S1	Summary Profile of On-Treatment Adverse Events Categorised as Malignancies		SAC
11.36	All Subjects	AE1	Summary of On-Treatment Adverse Events Categorised as Opportunistic Infections		SAC
11.37	All Subjects	TAB_S1	Summary Profile of On-Treatment Adverse Events Categorised as Opportunistic Infections		SAC
Laboratory - Haematology					
11.38	All Subjects	LB1	Summary of Haematology Changes from Baseline by Visit	Include baseline values	SAC
11.39	All Subjects	LB3	Summary of Haematology Shifts from Baseline Relative to Normal Range by Visit		SAC

CONFIDENTIAL

205667

No.	Population	IDSL / TST ID / Example Shell	Title	Programming Notes	Deliverable [Priority]
Safety : Tables					
11.40	All Subjects	LB3	Summary of Haematology Shifts from Baseline Relative to PCI Criteria by Visit		SAC
Laboratory – Clinical Chemistry					
11.41	All Subjects	LB1	Summary of Clinical Chemistry Changes from Baseline by Visit	Include baseline values	SAC
11.42	All Subjects	LB3	Summary of Clinical Chemistry Shifts from Baseline Relative to Normal Range by Visit		SAC
11.43	All Subjects	LB3	Summary of Clinical Chemistry Shifts from Baseline Relative to PCI Criteria by Visit		SAC
ECG					
11.43	All Subjects	EG1	Summary of ECG Findings by Visit		SAC
11.45	All Subjects	EG2	Summary of ECG Values by Visit		SAC
11.46	All Subjects	EG2	Summary of Change from Baseline in ECG Values by Visit	Include baseline values	SAC
Vital Signs					
11.47	All Subjects	VS1	Summary of Vital Signs by Visit		SAC
11.48	All Subjects	VS1	Summary of Change from Baseline in Vital Signs by Visit	Include baseline values	SAC
Injection Pain Assessments					
11.49	All Subjects	TAB_S3	Summary of Injection Pain – VAS Scores (mm)	By Visit and time point post-injection (injection, 1 hr post, 24 hrs post)	SAC
11.50	All Subjects	TAB_S4	Summary of Injection Pain – Categorical Pain Assessment	By Visit and time point post-injection (injection, 1 hr post, 24 hrs post)	SAC

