		Liquid Safety Syringe (N=XX)
1	All Events >= 1 event [1]	xx/xx (x%)
	1 event	xx (x%)
	2 events	xx (x%)
	3 events	xx (x%)
	>=4 events	xx (x%)
2	Serious Events >= 1 event [1]	xx/xx (x%)
3	Events considered related to investigational product >= 1 event [1]	xx/xx (x%)
4	Intensity [1]	
	Mild	xx/xx (x%)
	Moderate	xx/xx (x%)
	Severe	xx/xx (x%)
5	Outcome [1]	
	Recovered/Resolving	xx/xx (x%)
	Recovering/Resolving	xx/xx (x%)
	Not recovered/Not Resolved	xx/xx (x%)
	Recovered/Resolved with sequelae	xx/xx (x%)
	Fatal	xx/xx (x%)

[1] Information presented as number of events / number (%) subjects with at least one event. Subjects may be counted in more than one row.

[2] Cardiac History=Yes includes all subjects with any past medical condition under Cardiac Disorders.

[3] Unable to categorise time since last dose as event time not reported.

userid: /arenv/arprod/compound/study/final/drivers/drivename.sas DDMMYYYY HH:MM

Example TAB_S1 (Cont.)
 Protocol: MID205667
 Population: All Subjects (Safety)

Table X.X

Summary Profile of On-Treatment Adverse Events Defined by the Investigator as Allergic (Type I Hypersensitivity) Reactions

		Liquid Safety Syringe (N=XX)
6	Action Taken [1]	
	Study treatment withdrawn	xx/xx (x%)
	Dose reduced	xx/xx (x%)
	Dose increased	xx/xx (x%)
	Dose not changed	xx/xx (x%)
	Dose interrupted/delayed	xx/xx (x%)
	Not applicable	xx/xx (x%)
7	Cardiac History [1][2]	
	Yes	xx/xx (x%)
	No	xx/xx (x%)
8	Anaphylaxis Criteria Met	
	Anaphylactic Criterion 1	xx/xx (x%)
	Anaphylactic Criterion 2	xx/xx (x%)
	Anaphylactic Criterion 3	xx/xx (x%)
9	No. doses prior to event [1]	
	1	xx/xx (x%)
	2	xx/xx (x%)
	3	xx/xx (x%)
	etc.	
10	No. doses prior to first event	
	1	xx (x%)
	2	xx (x%)
	3	xx (x%)
	etc.	

[1] Information presented as number of events / number (%) subjects with at least one event. Subjects may be counted in more than one row.

[2] Cardiac History=Yes includes all subjects with any past medical condition under Cardiac Disorders.

[3] Unable to categorise time since last dose as event time not reported.

userid: /arenv/arprod/compound/study/final/drivers/drivername.sas DDMMYYYY HH:MM

Example TAB_S1 (Cont.)
 Protocol: MID205667
 Population: All Subjects (Safety)

Table X.X

Summary Profile of On-Treatment Adverse Events Defined by the Investigator as Allergic (Type I Hypersensitivity) Reactions

	Liquid Safety Syringe (N=XX)
11	Time since last dose to event onset [1]
	<=1 hr xx/xx (x%)
	1-<6 hrs xx/xx (x%)
	6-<24 hrs xx/xx (x%)
	>=24 hrs xx/xx (x%)

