	Missing [3] xx/xx (x%)
12	Time since last dose to first event onset
	<=1 hr xx (x%)
	1-<6 hrs xx (x%)
	6-<24 hrs xx (x%)
	>=24 hrs xx (x%)
	Missing [3] xx (x%)
13	No. symptoms associated with event [1]
	0 symptoms xx/xx (x%)
	1 symptom xx/xx (x%)
	2-5 symptoms xx/xx (x%)
	>5 symptoms xx/xx (x%)
14	Symptoms [1]
	ABDOMINAL xx/xx (x%)
	ANGIOEDEMA xx/xx (x%)
	ARTHRALGIA xx/xx (x%)
	Etc.

[1] Information presented as number of events / number (%) subjects with at least one event. Subjects may be counted in more than one row.

[2] Cardiac History=Yes includes all subjects with any past medical condition under Cardiac Disorders.

[3] Unable to categorise time since last dose as event time not reported.

userid: /arenv/arprod/compound/study/final/drivers/drivername.sas DDMMYYYY HH:MM

CONFIDENTIAL

205667

Programming Notes:-

Remove footnotes that are not relevant for the table.

Sections 1 - 6, 9, 10: Create for all adverse events of special interest

Sections 9 and 10: For studies longer than 1 year can consider the following categories: 1, 2, 3, 4, 5, 6, 7-12, 13-18, 19-24, >24

Section 7: Only for the following adverse events of special interest
Serious Cardiac, Vascular and Thromboembolic Events
Serious Ischemic Events

Section 8: Only for the following adverse events of special interest
Anaphylaxis
Systemic - Allergic (Type I Hypersensitivity)

Sections 11 - 14: Only for the following adverse events of special interest
Anaphylaxis
Systemic - Allergic (Type I Hypersensitivity) and Other Systemic
Systemic - Allergic (Type I Hypersensitivity)
Systemic - Other Systemic
Local Injection Site Reactions

CONFIDENTIAL

205667

Example TAB_S2
Protocol: MID205667
Population: All Subjects (Safety)

Page 2 of 2

Table X
Summary of Binding Antibody Results by Visit

Visit	Assay Result	Liquid Safety Syringe (N=XX)
WEEK 0	n	X
	NEGATIVE	X (XX%)
	POSITIVE	X (XX%)
WEEK 12/EARLY WITHDRAWAL	n	X
	NEGATIVE	X (XX%)
	POSITIVE	X (XX%)
	Titre value	Min. X
		Median X.X
		Max. X

userid: /arenv/arprod/compound/study/final/drivers/drivername.sas DDMMYYYY HH:MM

Example TAB_S3
Protocol: MID205667
Population: All Subjects (Safety)

Table X
Summary of Injection Pain - VAS Scores (mm)

Treatment: Liquid Safety Syringe (N=XX)

Visit	N	Planned Relative Time	n	Mean	SD	Median	Min.	Max.
WEEK 0	XX	INJECTION	XX	X.X	X.XX	X.X	XX	XX
		1 HR POST INJECTION	XX	X.X	X.XX	X.X	XX	XX
		24 HRS POST INJECTION	XX	X.X	X.XX	X.X	XX	XX
WEEK 4	XX	INJECTION	XX	X.X	X.XX	X.X	XX	XX

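### TAB_S1 defines Cardiac History from past conditions only, so a subject whose cardiac conditions are all recorded as current would be counted under No in Tables 11.31 and 11.33

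*SAP*

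**What the plan says.** SAP 14.8.6 assigns shell TAB_S1 to Table 11.31, "Summary Profile of On-Treatment Adverse Events Categorised as Serious Cardiac, Vascular and Thromboembolic Events", and to Table 11.33, "Summary Profile of On-Treatment Adverse Events Categorised as Serious Ischemic Events". Row group 7 of that shell splits the events into Yes and No by cardiac history. The programming note that begins "Section 7: Only for the following adverse events of special interest" confines this row group to those two event types.

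The rule for the split is footnote [2] of the shell: "Cardiac History=Yes includes all subjects with any past medical condition under Cardiac Disorders".

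In SAP 14.8.1, past and current conditions are two separate displays: Table 6.15, "Summary of Past Medical Conditions", and Table 6.16, "Summary of Current Medical Conditions". Table 2 in SAP 6.1 names both categories where both are meant.

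On entry, protocol 5.2 criterion 5 lists cardiovascular disease among the excluded conditions, but only where clinically significant and in the group that ends with "any other system abnormalities that are uncontrolled with standard treatment".

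**The concern.** The cardiac history row lets a reader see whether a serious cardiovascular or ischemic event arose in someone who already had heart disease. Ongoing disease is at least as relevant to that question as resolved disease. If *past* carries the meaning it has in Tables 6.15 and 6.16, the row leaves out ongoing disease unless the subject also has a past cardiac entry. An event in a subject with, say, controlled atrial fibrillation and nothing else cardiac on record would then sit beside events in subjects with no heart disease at all.

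The study has one arm and few expected events, so a single misplaced event could make up the whole content of the row.

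**Working it through.** **Is there another definition?** SAP 11.1.1 (events of special interest), 14.4.2 and 14.4.4 (derived data), 14.8.6 (display list) and the TAB_S1 programming notes do not define cardiac history or add current conditions to it. Footnote [2] is the only rule a programmer has.

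**Applying the rule to the four possible records**

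| Past cardiac condition | Current cardiac condition | Footnote as written | With *past or current* |
|---|---|---|---|
| yes | no | Yes | Yes |
| yes | yes | Yes | Yes |
| no | yes | **No** | **Yes** |
| no | no | No | No |

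Only the third line changes.

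**Can such subjects be in the study?** Yes. Criterion 5 turns on disease being uncontrolled, so controlled ongoing cardiac disease is not excluded by it. Protocol 7.2.1 collects medical history and cardiovascular history at Visit 1.

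**How often could it matter?** The plan gives no figure for this, so there is none to reproduce. The inputs are:

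- Subjects: 55 enrolled (protocol 9.2.1).
- Window: Tables 11.31 and 11.33 show on-treatment events. SAP 14.2.1.1 ends that phase 28 days after the first dose.
- Event rate: not in the documents. Assumed 1 to 3 serious events per 100 person-years.

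Exposure = 55 × 28 / 365.25 = 4.2 person-years.

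Chance of at least one event = 1 − exp(−rate × exposure):

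| Assumed rate per 100 person-years | Expected events | Chance of at least one |
|---|---|---|
| 1 | 0.04 | 4% |
| 2 | 0.08 | 8% |
| 3 | 0.13 | 12% |

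These are chances of *any* event. For a misclassified one, the expected count must be multiplied by the share of events that fall in subjects whose cardiac conditions are all current. The documents do not give that share. It cannot exceed 1, so 4% to 12% is a ceiling at these rates.

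**The case against.** The strongest defence has three parts.

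*The wording may be loose.* The footnote says *includes*, not *only*; it sits in an example shell that looks like a reused template; and *past* might simply mean pre-existing. This lowers the certainty that current conditions would be dropped. It does not remove the problem, because the SAP uses the two words as separate categories and nothing tells the programmer to add current conditions.

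*Nothing is lost.* Listing 12 gives each subject's medical conditions, Listings 28 and 29 give each such event, and the protocol requires event-specific cardiovascular CRF pages. With no event or one expected, the case would be read from these. This stands, and it is why the point is minor.

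*Stronger readings go too far.* Four are tempting, and the documents do not support them:

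- That every event in a subject with ongoing heart disease is misplaced. Any past cardiac entry still gives Yes.
- That the relevant exposure is the full 12 weeks. That would be 55 × 84 / 365.25 = 12.6 person-years and a 12% to 32% chance of any event at the same rates. The two tables are restricted to on-treatment events, and the SAP's window for these is 28 days from first dose. The larger figures would apply only if that window were extended.
- That an event under No would read as a product effect. Row group 3 of the same shell reports investigator-assessed relatedness separately.
- That the Yes and No rows need their own denominators. Footnote [1] describes the entries as counts of events and of subjects with events, as in the intensity and outcome rows, and nothing presents row group 7 as incidence within each group. Adding group sizes is a presentation preference.

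**Conclusion.** The point holds in a narrow form. The footnote, read with the SAP's own use of *past* and *current*, puts a subject with only current cardiac conditions in the wrong row of Tables 11.31 and 11.33. All other subjects are classified as intended.

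The consequence is small. The primary endpoint is untouched, no hypothesis is tested, and only the Yes/No split within two descriptive tables can change. The conclusion on wording rests on taking *past* in the footnote to mean what it means in Table 6.15. The size rests on the assumed event rates and on the 28-day window as the SAP states it. The case for acting is that the stated rule gives a wrong classification and is trivial to correct, not that a visible effect is likely.

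**What to change.** In TAB_S1 footnote [2], insert *or current* after *past*, so that any past or current condition coded under Cardiac Disorders gives Yes. Derive it from the medical history collected before the first dose.

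The condition need not be dated to Visit 2: medical history is scheduled at Visit 1, and the Visit 2 procedures in protocol 7.2.2 do not include it. The rest of the shell can stay as it is.

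The cost is two words in the SAP and the matching line of the derivation. No new data are needed and no downside is apparent.
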